**Procedures for handling patients incorrectly initiated on investigational product:**

Patients who do not meet the inclusion/exclusion criteria should not, under any circumstances, be enrolled or receive study medication. There can be no exceptions to this rule.

Where patients that do not meet the inclusion/exclusion criteria are enrolled in error or incorrectly started on treatment, or where patients subsequently fail to meet the study criteria post initiation, the Investigator should inform the Study Physician immediately.

Any patient who is found to have failed to comply with all the selection criteria, but has not started treatment, will be removed from the study following completion of safety follow-up activities.

Any patient started on treatment in error, as he/she has subsequently been found to have failed to comply with all the selection criteria, will undergo a risk/benefit assessment by the SRC; if the patient is judged to be receiving clinical benefit, the investigator may choose to continue to dose them with the investigational drug.

Every effort should be made to keep all patients, whether eligible or ineligible, in the study until completion of safety follow-up activities.

The Study Physician is to ensure all such contacts are appropriately documented.

## 4 SAFETY – CORE

### 4.1 Definitions of Adverse Events and Serious Adverse Events

The Investigator is responsible for recording all AEs observed during the study (from time of signed consent, washout, treatment, and follow-up) period.

Definition of AE: An AE is any new untoward medical occurrence or worsening of a pre-existing medical condition in a subject or clinical investigation subject administered a pharmaceutical product and which does not necessarily have a causal relationship with this treatment.

Treatment-emergent adverse events: An AE occurring after dosing and within 30 days of last dose.

Definition of Serious Adverse Event (SAE): An SAE, experience or reaction, is any untoward medical occurrence (whether considered to be related to study drug or not) that at any dose:

- Results in death.
- Is life-threatening (the subject is at a risk of death at the time of the event; it does not refer to an event which hypothetically might have caused death if it were more severe).
- Requires inpatient hospitalization or prolongation of existing hospitalization: Hospitalizations are defined as initial or prolonged admissions that include an overnight stay. Hospitalization or prolonged hospitalization for technical, practical or social reasons, in the absence of an adverse event is not an SAE. Hospital admissions and/or surgical operations planned before or during a study are not considered AEs if the illness or disease existed before the subject was enrolled in the study, provided that it did not deteriorate in an unexpected way during the study.
- Results in persistent or significant disability/incapacity.
- Is a congenital abnormality/birth defect.
- Other: Medically significant events, which do not meet any of the criteria above, but may jeopardize the subject and may require medical or surgical intervention to prevent one of the other serious outcomes listed in the definition above. Examples of such events are blood dyscrasias (e.g. neutropenia or anemia requiring blood transfusion, etc.) or convulsions that do not result in hospitalization.

An Adverse Drug Reaction (ADR) is defined as all noxious and unintended responses to a medicinal product related to any dose. An Unexpected Adverse Drug Reaction is defined as any adverse reaction, the nature of which is not consistent with the applicable product information.

Each AE is to be evaluated for duration, severity, seriousness and causal relationship to the investigational drug. The action taken and the outcome must also be recorded.

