### **1.7.2.2 Potential Risks**

The clinical, pre-clinical and emerging safety profile has not identified any risks that would preclude investigation of a RXC004 and nivolumab combination in an advanced cancer setting. At high exposures of RXC004 the preclinical toxicities that overlap with those commonly seen with PD-1 inhibitors are those that affect the gut mucosa.

Checkpoint inhibitors including anti PD-1, as well as antibodies directed against PDL-1 and CTLA-4, boost the endogenous immune responses directed against tumours. AEs seen with checkpoint inhibitors are frequently due to immune-mediated mechanisms and can occur in any organ system. The most commonly seen immune-mediated effects include GI effects (e.g. diarrhoea or colitis), pneumonitis, hepatic events, skin rashes and dermatitis and endocrinopathies (including hypo and hyper-thyroidism).

The safety of nivolumab administered as a single agent or in combination with ipilimumab in patients with mCRC was evaluated in the CHECKMATE-142 study (NCT02060188). For single-agent nivolumab, the most frequent SAEs reported in  $\geq 2\%$  of patients were colitis/diarrhea, hepatic events, abdominal pain, acute kidney injury, pyrexia, and dehydration. The most common AEs reported in monotherapy (in  $\geq 20\%$  of patients) were fatigue, diarrhoea, pyrexia, musculoskeletal pain, abdominal pain, pruritus, nausea, rash, decreased appetite, and vomiting. {Overman, 2017 Ref 34}

Immune-mediated AEs that can occur during treatment with nivolumab can be seen weeks or months after discontinuation of treatment. Symptoms of these events will be monitored throughout treatment (e.g. diarrhoea, rash, and neuropathy). Laboratory assessments will check for elevated liver enzymes, kidney and thyroid function, electrolytes, glucose and blood counts.

A detailed description of the chemistry, pharmacology, efficacy, and safety of nivolumab is provided in the nivolumab prescribing information.

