## **4.2 Reporting of Adverse Events, Serious Adverse Events and Dose Limiting Toxicities**

TEAEs reported during the study will be coded using a Medical Dictionary for Regulatory Activities (MedDRA) dictionary. Incidence of treatment-emergent adverse events will be summarised by disease and cohort and the following:

- System organ class and preferred term
- System organ class, preferred term and severity

These summaries will be presented for the following subsets:

- SAEs
- All AEs
- Drug-related AEs
- AEs leading to treatment discontinuation

For tables reporting AEs by severity, if a patient has multiple occurrences of an AE with the same organ class and preferred term, the most severe event will be presented.

All SAEs will be recorded on the SAE Report form, the Adverse Events form in the CRF, and source documents. Criteria for documenting the relationship to study drug as well as severity and outcome will be the same as those previously described.

All SAEs that are spontaneously reported within 30 days of a patient's last dose of RXC004 (for Module 1) or 90 days of a patient's last dose of nivolumab (for Module 2) are to be collected and reported as previously described.

The original CRF pages should be returned immediately to the CRF binder. The information must include at least the following:

- Name, address and telephone number of the reporting Investigator.
- Investigational product and study code.
- Patient identification number, sex and age at study entry.
- Description of the AE, measures taken and outcome.
- Preliminary classification of causal relationship by the Investigator.

The Principal Investigator (or designee) will notify IQVIA within 24 hours of identifying a DLT or SAE, whether related or unrelated to investigational drug, see Section 3.

Additional follow-up information should be completed on an SAE follow-up form with a copy sent to the Sponsor or IQVIA and the original placed in the SAE section of the CRF binder.

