#### **4.2.2 Follow-Up of Adverse Events**

Any AEs observed from the time of consent/randomisation up to the end of the study will be followed up to resolution. Resolution means that the patient has returned to a baseline state of health or the Investigator does not expect any further improvement or worsening of the AE. All AEs that occur after the patient completed a clinical study should also be reported to IQVIA Clinical within 30 days of the last dose of study drug.

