## 9.6 Safety

### 9.6.1 Adverse Events

Treatment-emergent adverse events are defined as AEs that first occurred or worsened in severity after the first administration of the study drug and within 30 days of last dose of RXC004 in the case of module 1 and within 90 days of last dose of nivolumab for module 2. Adverse event summaries will include incidence of treatment-emergent AEs by MedDRA preferred term and system organ class, SAEs including deaths, AEs that led to study drug discontinuation, AEs leading to death, treatment related AEs and AEs by maximum severity..

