## **B. Adverse Events**

Adverse events will be coded using MedDRA version 24.1. AEs are graded using the National Cancer Institute (NCI) Common Terminology Criteria for Adverse Events (CTCAE) Version 5.0.

A treatment-emergent AE (TEAE) is defined as AEs that first occurred or worsened in severity after the first administration of the study treatment (RXC004 or Nivolumab) and within 30 days of last dose of RXC004 in the case of Module 1 and Module 3 and within 90 days of last dose of Nivolumab for Module 2.

If relationship to RXC004 or Nivolumab is missing, the event will be conservatively treated as related to the corresponding study treatment. Missing CTCAE grade will be summarized as separate category.

All AEs will be listed by module, dose cohort and patient, detailing the verbatim term given by the investigator, the preferred term (PT), system organ class (SOC), onset date, stop date, CTCAE grade, relationship to RXC004, relationship to Nivolumab (Module 2 only), action taken with RXC004, action taken with Nivolumab (Module 2 only), other action taken, dose limiting toxicity (Y/N), caused by disease progression (Y/N) and seriousness. Dose limiting toxicity.

An overall AE summary will be present by the number and percent of patients for each module separately with the following:

- All AEs
- All TEAEs
- Dose limiting toxicity (DLTs) (Module 1 and 2 only)
- RXC004-related TEAEs

- Any TEAE of CTCAE of grade 3 or higher
- Any TEAE of CTCAE of grade 3 or higher related to RXC004
- Nivolumab-related TEAEs (Module 2 only)
- Any TEAE of CTCAE of grade 3 or higher related to Nivolumab (Module 2 only)
- Serious AEs
- RXC004-related SAEs
- Nivolumab-related SAEs (Module 2 only)
- TEAEs leading to RXC004 withdrawal
- TEAEs leading to Nivolumab withdrawal
- TEAEs leading to RXC004 reduction
- RXC004 related adverse event leading to death
- Nivolumab-related adverse event leading to death (Module 2 only)
- TEAEs leading to RXC004 interruption
- TEAEs leading to Nivolumab interruption
- AEs leading to death

The following AE summaries will be produced by system organ class (alphabetical order) and preferred term (descending order of the overall frequency) for each module separately:

- All TEAEs
- Serious AEs
- Grade 3 or higher TEAEs
- TEAEs leading to RXC004 withdrawal. This subset includes TEAEs with an Action Taken with RXC004 of “Drug Permanently Withdrawn” on the AE form.

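### The 30-day treatment-emergent window that Protocol Section 4.1 gives for all modules contradicts the 90-day Module 2 window in Section 9.6.1 and the SAP

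*Protocol*

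**What the plan says.** Four places set a time limit on adverse events after treatment, and they differ for Module 2.

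- **Protocol 4.1** (core, all modules) defines a treatment-emergent event as "An AE occurring after dosing and within 30 days of last dose". It names no module and does not say which drug's last dose counts. The same section also states: "The Investigator is responsible for recording all AEs observed during the study (from time of signed consent, washout, treatment, and follow-up) period".
- **Protocol 4.2** gives serious events in Module 2 a longer collection period, "or 90 days of a patient's last dose of nivolumab (for Module 2"). Non-serious events are not mentioned there.
- **Protocol 4.2.2** says that events arising after a patient has completed the study "should also be reported to IQVIA Clinical within 30 days of the last dose of study drug", again with no module distinction.
- **Protocol 9.6.1** and **SAP IX.B** end the Module 2 treatment-emergent window "within 90 days of last dose of nivolumab for module 2" and "within 90 days of last dose of Nivolumab for Module 2" respectively.

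Appendix 2 (Module 2 schedule) has safety follow-up visits 30 days after investigational product stops and 90 days after the last nivolumab dose, each with a 3-day tolerance. Its adverse-event row is marked at both.

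**The concern.** One term has two definitions for the same patients, and neither is superseded text. The definition in 4.1 is not idle: Section 4.2 goes on to promise incidence summaries of treatment-emergent events, which are the summaries that 9.6.1 and the SAP describe with the longer window.

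The disputed period is also where the protocol expects nivolumab events to appear. Section 1.7.2.2 says that immune-mediated events "can be seen weeks or months after discontinuation of treatment". Safety and tolerability is the primary objective for every module, and the incidence and severity of adverse events is the first safety endpoint listed in the SAP.

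Two things are at stake. First, an event on, say, day 60 after the last infusion may be treatment-emergent under the SAP and not under 4.1, however well it was captured. Second, a site that reads 4.1, 4.2 and 4.2.2 together could conclude that only serious events are wanted after day 30. If some sites read it that way and others follow Appendix 2, non-serious Module 2 events would be reported unevenly within a window that the analysis treats as uniform.

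**Working it through.** **Inputs.** Core window: 30 days after last dose (Protocol 4.1). Module 2 analysis window: 90 days after last nivolumab (Protocol 9.6.1, SAP IX.B). RXC004 may continue after nivolumab stops (Protocol 5.3.7 and Table 6). Planned Module 2 size: about 18 (Protocol 9.1).

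**Assumption.** The unspecified last dose in 4.1 is taken as the last dose of either agent.

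**Formula.** Let *d* be the number of days by which the last RXC004 dose follows the last infusion, with *d* = 0 if RXC004 stops on or before that day. Counting from the last infusion, the core window closes on day *d* + 30 and the analysis window on day 90. The gap is 90 − (*d* + 30) = 60 − *d*.

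| *d* (days) | Core window closes | Analysis window closes | Gap |
|---|---|---|---|
| 0 | day 30 | day 90 | 60 days |
| 28 | day 58 | day 90 | 32 days |
| 60 | day 90 | day 90 | 0 days |
| 90 | day 120 | day 90 | −30 days |

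If both agents stop within one undelayed 28-day cycle, *d* lies between 0 and about 28, so the gap is roughly 32 to 60 days. The upper bound over the module is 18 × 60 = 1,080 patient-days classified differently.

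The last row shows the conflict reversing. With *d* above 60, the nivolumab-only anchor in 9.6.1 and the SAP closes before the core window. With *d* at 90 or more, it closes while the patient may still be taking RXC004. A patient who received only the Cycle 0 RXC004 dose has no nivolumab date to count from.

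**The 4.2.2 sentence.** It concerns events after study completion. If a Module 2 patient completes safety follow-up at the 90-day visit and RXC004 did not outlast the last infusion by 60 days or more, the 30 days have already passed when the sentence begins to apply. For that patient it is either empty or is read as a general 30-day limit. It is also unclear whether the 30 days limit the onset of the event or the time allowed to report it.

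**Is there a planned collection point after day 30?** Yes. Appendix 2 marks adverse events at the 90-day visit, and the open question in Section 4.1 asks about problems since the previous visit, so that visit covers the interval back to the 30-day visit.

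**The case against.** The strongest reply is that a treatment-emergent definition is an analysis label and not a limit on collection. Protocol 9.2.3 leaves analysis detail to the SAP, the SAP says that it governs the safety analysis, and the SAP agrees with 9.6.1 on 90 days, so the planned Module 2 analysis has a single window. Collection is covered by the recording duty in 4.1 and by the 90-day visit. The sentence in 4.2.2 adds a duty after completion, and a patient still awaiting the 90-day visit has arguably not completed. Late serious events have 90 days already. The formal Module 2 dose-limiting toxicity window, Cycle 1 Days 1 to 28, is untouched.

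Most of this stands, and it limits the consequence. A reader might infer from 4.1 and 4.2.2 that Section 4 ends adverse-event reporting at 30 days for every module, so that late non-serious immune events in Module 2 go uncollected. The documents do not support that: 4.1 requires recording through follow-up, 4.2 carries serious events to 90 days, and Appendix 2 schedules collection at day 90. Nor can it be said that the SAP's tables will be headed as 90-day tables, since no table shells are shown.

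The reply does not remove the contradiction. The core section still states a different window for the same term, and extending serious events alone in 4.2 invites the reading that other events stop at 30 days.

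**Conclusion.** The inconsistency is confirmed and should be corrected. For Module 2, 4.1 contradicts 9.6.1 and SAP IX.B, and 4.2.2 adds an ambiguous 30-day sentence. The consequence is inconsistent classification and possibly uneven reporting of non-serious events after day 30, not certain loss.

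The size is a gap of at most 60 of the 90 days (67%), when the core rule's last dose is the last infusion. It shrinks day for day as RXC004 continues and reverses beyond 60 days. This rests on reading last dose as the last dose of either agent.

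The effect on reported incidence cannot be estimated, because the documents give no rate of late non-serious events and no probability that one is missed. As a scale only, one patient is 1/18 = 5.6 percentage points of the module or 1/6 = 16.7 points of a full cohort of six, and only if that patient had no earlier event counted at the same level. Neither figure should be quoted as an expected bias.

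**What to change.** Reconcile Protocol 4.1, 4.2.2 and 9.6.1 and SAP IX.B to one window per module, applied to all adverse events and not only serious ones.

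- **Modules 1 and 3:** 30 days after the last RXC004 dose. The SAP already states this for Module 3. Section 9.6.1 gives Module 3 no window, and the serious-event sentence in 4.2 does not name Module 3 either, so copying 9.6.1 into Section 4 would not be enough.
- **Module 2:** keep the planned 90 days after last nivolumab, and state the anchor so that events during continued RXC004, or within 30 days of its end, are not dropped. One form is the later of 90 days after the last nivolumab dose and 30 days after the last RXC004 dose. This also covers a patient who never reached nivolumab.
- **4.2.2:** state whether the limit refers to onset or to reporting time, and use the same module-specific windows.

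The cost is a few sentences in each document. No visit is added: either end of the later-of rule falls on a safety visit already in Appendix 2, taking the 30-day visit to follow the end of RXC004 when that drug is stopped last.

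If Module 2 data have already been collected, apply the single window in the analysis and state in the study report how non-serious events from days 31 to 90 were collected.

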### **Severity**

The severity of the AE will be characterized as “mild, moderate or severe” according to the following definitions:

- Mild (Grade 1) events are usually transient and do not interfere with the subject’s daily activities.
- Moderate (Grade 2) events introduce a low level of inconvenience or concern to the subject and may interfere with daily activities.
- Severe (Grade 3) events interrupt the subject’s usual daily activity.
- Life-threatening (Grade 4) - Life-threatening consequences; urgent intervention indicated.
- Death (Grade 5) related to AE.

### **Relationship**

The causal relationship between the study medication and the AE has to be characterized as unrelated, unlikely, possible, probable or unknown (unable to judge).

Events can be classified as “unrelated” if there is not a reasonable possibility that the study medication caused the AE. An “unlikely” relationship suggests that only a remote connection exists between the study drug and the reported AE. Other conditions, including chronic illness, progression or expression of the disease state or reaction to concomitant medication, appear to explain the reported AE.

A “possible” relationship suggests that the association of the AE with the study medication is unknown; however, the AE is not reasonably supported by other conditions.

A “probable” relationship suggests that a reasonable temporal sequence of the AE with drug administration exists and, in the Investigator’s clinical judgment, it is likely that a causal relationship exists between the drug administration and the AE, and other conditions (concurrent illness, progression or expression of disease state or concomitant medication reactions) do not appear to explain the AE.

### **Adverse Events Based on Signs and Symptoms**

All AEs spontaneously reported by the patient, in diary or reported in response to the open-ended and non-leading verbal questioning from the study personnel (e.g., “How are you feeling?” “Have you had any health problems since the previous visit/you were last asked?”), or revealed by observation will be collected and recorded in the CRF. When collecting AEs, it is preferred to record the diagnoses (when possible) instead of recording a list of signs and

symptoms. However, if a diagnosis is known and there are other signs or symptoms that are not generally part of the diagnosis, the diagnosis and each sign or symptom will be recorded separately.

### **Adverse Events Based on Examinations and Tests**

The results from protocol mandated laboratory tests, vital signs, ECGs and other safety assessments will be summarised in the Clinical Study Report. Deterioration as compared to baseline in these parameters will therefore only be reported as AEs if they fulfil any of the criteria for a SAE, a DLT or are the reason for discontinuation of treatment with the investigational product unless clearly due to progression of disease under study (see Disease progression).

If deterioration in a laboratory value, vital sign, ECG or other safety assessment is associated with clinical signs and symptoms, the sign or symptom will be reported as an AE and the associated laboratory result or other finding will be considered as additional information. Wherever possible the reporting Investigator uses the clinical, rather than the laboratory term (e.g., anaemia versus low haemoglobin value). In the absence of clinical signs and symptoms, clinically relevant deteriorations in non-mandated parameters should be reported as AE(s).

Deterioration of a laboratory value that is unequivocally due to disease progression should not be reported as an AE.

Any new or aggravated clinically relevant abnormal medical finding at a physical examination as compared with the baseline assessment will be reported as an AE.

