### **7.2.2 Clinical Laboratory Evaluations**

The Investigator, IQVIA Clinical Medical Monitor, and Redx Chief Medical Officer (CMO) will review clinical laboratory tests for results of potential clinical significance at all the time points throughout the study. The Investigator will evaluate any change in laboratory values. If the Investigator determines a laboratory abnormality to be clinically significant, it is considered a laboratory AE; however, if the abnormal laboratory value is consistent with a current diagnosis, it may be documented accordingly.

Table 8 includes a list of analytes to be collected during the study.

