- TEAEs leading to RXC004 reduction. This subset includes TEAEs with an Action Taken with RXC004 of “Dose reduced” on the AE form
- TEAEs leading to RXC004 interruption. This subset includes TEAEs with an Action Taken with RXC004 of “Dose interrupted” on the AE form
- TEAEs leading to Nivolumab withdrawal (Module 2 only). This subset includes TEAEs with an Action Taken with Nivolumab of “Drug Permanently Withdrawn” on the AE form.
- TEAEs leading to Nivolumab interruption (Module 2 only). This subset includes TEAEs with an Action Taken with Nivolumab of “Dose interrupted” on the AE form
- TEAEs related to RXC004. This table will include TEAEs with a drug relationship of “Possibly Related” or “Probably Related” to RXC004.
- TEAEs related to Nivolumab (Module 2 only). This table will include TEAEs with a drug relationship of “Related” to Nivolumab.
- SAEs related to RXC004
- SAEs related to Nivolumab (Module 2 only)
- Grade 3 or higher TEAEs related to RXC004
- Grade 3 or higher TEAEs related to Nivolumab (Module 2 only)
- AEs leading to death

- AEs considered as dose-limiting toxicity (DLT) (Module 1 and 2 only)
- TEAEs by maximum CTCAE grade
- TEAE by PT
- Treatment Related TEAE by PT.

At each level of summarization, a patient will be counted once if he/she reported one or more events. The maximum CTCAE grade will be taken for the purposes of the summaries by grade.

In addition, all deaths as collected on the Death eCRF page will be present in a data listing.

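### Protocol 4.1 and 7.2.2 give different rules for when a mandated laboratory abnormality is an AE, so laboratory-type entries in the SAP's TEAE tables can depend on which section a site follows

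*Protocol*

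**What the plan says.** Protocol 4.1, under its sub-heading on examinations and tests, starts from the premise that "The results from protocol mandated laboratory tests, vital signs, ECGs and other safety assessments will be summarised in the Clinical Study Report". It concludes that deteriorations from baseline in those measures "will therefore only be reported as AEs if they fulfil any of the criteria for a SAE", or are dose-limiting, or led to study drug being stopped, and not where progression is clearly the cause. Two provisos follow. If there are associated symptoms, "the sign or symptom will be reported as an AE and the associated laboratory result or other finding will be considered as additional information". If there are none, clinically relevant worsening is still reportable for parameters that the protocol does not mandate.

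Protocol 7.2.2, which introduces the required analytes of Table 8, says: "If the Investigator determines a laboratory abnormality to be clinically significant, it is considered a laboratory AE". It adds one carve-out: "if the abnormal laboratory value is consistent with a current diagnosis, it may be documented accordingly". Section 7.2.1 lists laboratory testing among the sources of reportable AEs and applies no filter.

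The primary objective in every module is safety and tolerability, and SAP III.B makes AE incidence and severity a safety endpoint. SAP IX.B builds its TEAE tables from AE records. For example: "TEAEs leading to RXC004 interruption. This subset includes TEAEs with an Action Taken with RXC004 of" dose interrupted on the AE form.

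**The concern.** For mandated laboratory tests, 4.1 has a closed list of three triggers, while 7.2.2 needs only the investigator's judgement of clinical significance. The sections do not refer to each other, neither is given precedence, and the SAP tabulates whatever reached the AE form. Two sites could each follow the protocol and record the same laboratory value differently.

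The tables at risk are those that attach grade, causality or action taken to an event. Dose interruption and dose reduction are not triggers in 4.1. An asymptomatic laboratory change that led the investigator to hold the drug could therefore have no AE record under 4.1 and a full one under 7.2.2.

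**Working it through.** **Step 1: do the rules cover the same tests?** Yes. Section 4.1 restricts protocol-mandated tests and 7.2.2 concerns the required analytes of Table 8. The conflict rests on these two sections. Section 7.2.1 points the same way, but it can be read as saying how AEs are found rather than what counts as one.

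**Step 2: where do they differ?**

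| Laboratory finding judged clinically significant | Under 4.1 | Under 7.2.2 |
|---|---|---|
| Serious, a DLT, or the reason for discontinuation | AE | AE |
| Accompanied by signs or symptoms | The symptom is the AE | AE, or documented under the diagnosis |
| Asymptomatic, no trigger met, explained by a current diagnosis | Not an AE | May be documented under the diagnosis |
| Asymptomatic, no trigger met, not so explained | Not an AE | Laboratory AE |

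Only the last row is a direct contradiction.

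**Step 3: can that row be occupied?**
- *Grade 3 neutropenia.* Protocol 5.2.6 and 5.3.6 list it as a DLT only with fever or systemic infection. Without these it meets no 4.1 trigger, unless it is judged a DLT by the SRC or medically significant under the SAE definition, holds dosing for more than 14 days in Module 1, or leads to discontinuation.
- *Module 3.* Section 5.4 defines no DLT, and SAP IX.B limits DLT tables to Modules 1 and 2. (Protocol 9.1 mentions DLT evaluability for Module 3 without a definition.) That leaves two usable triggers. An asymptomatic Grade 3 ALT rise shows the effect. Table 4 lists it for discontinuation in Module 1, so it is an AE under 4.1. Table 7 has no hepatic row, so in Module 3 section 4.1 captures it only if it is serious or treatment is in fact stopped.
- *After the DLT window in Modules 1 and 2.* The DLT trigger has lapsed there too.

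**Step 4: which outputs move?**
- Exposed (SAP IX.B): all TEAEs, related TEAEs, Grade 3 or higher TEAEs, and TEAEs leading to RXC004 reduction or interruption, in their laboratory-type entries.
- Not exposed: SAEs and DLTs; RXC004 dose changes with reasons, counted from dosing data (SAP IX.A); laboratory grades derived from results, shift tables and counts of clinically significant evaluations (SAP IX.C).

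**Step 5: size.** The plan states no figure to reproduce. One patient moves a rate by 100/n points:
- n = 6 (Module 3 arm, protocol 5.4.4): 100/6 = 16.7 points.
- n = 25 (Module 1 patients dosed, protocol 5.4.3): 100/25 = 4.0 points.

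These are upper limits per patient. SAP IX.B counts a patient once at each level of summary, so a row moves only if that patient has no other qualifying TEAE in it.

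The documents give no frequency. Let q be the assumed share of patients with an event in the contradictory row. The chance of at least one is 1 − (1 − q)^n, and the expected number is n × q.

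| Assumed q | n = 6: chance; expected | n = 25: chance; expected |
|---|---|---|
| 5% | 26.5%; 0.3 | 72.3%; 1.25 |
| 10% | 46.9%; 0.6 | 92.8%; 2.5 |
| 20% | 73.8%; 1.2 | 99.6%; 5.0 |
| 30% | 88.2%; 1.8 | >99.9%; 7.5 |

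For instance, 1 − 0.95^6 = 0.265. The table is an illustration and does not estimate q.

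**The case against.** The best defence is that 4.1 gives a reason for its narrow rule: mandated results are summarised in their own right, so recording them again as AEs adds little. The SAP keeps that promise in IX.C. Section 4.1 also reaches further than it first appears. Within the DLT window, clinically significant non-haematological laboratory changes of Grade 3 or higher are DLTs, the SAE definition includes medically significant events, and symptoms are AEs in their own right. CRF completion guidance, which is not among the documents, may already settle the matter for sites.

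This shows that the affected class is small and that the laboratory signal is not lost. It does not show which section governs. The shift tables and clinical-significance counts carry neither causality nor action taken, so they do not replace the AE tables. Divergence between sites is an inference from the two texts, not something the documents report.

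Three stronger readings are tempting, and the documents do not support them:
- *Laboratory-driven dose interruptions disappear from the report.* They do not. SAP IX.A counts dose changes and their reasons from dosing data. Only the TEAE-based rows can miss them.
- *Tables 4, 6 and 7 require interruption or reduction for laboratory toxicities that 4.1 then excludes.* The Grade 3-4 rows in question stand under a heading for other adverse events, so they presuppose an AE. No row names a Table 8 analyte and directs interruption or reduction of RXC004 for it.
- *The modules become non-comparable.* The study is non-comparative and reports modules separately. Dysgeusia, the toxicity Module 3 singles out, is found by questioning and is untouched by a laboratory rule.

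**Conclusion.** The inconsistency is real and worth correcting, but it is confined to one class of laboratory finding. A reader might infer that primary-safety AE rates as a whole depend on the section followed. That goes too far, because everything outside the last row of the step 2 table is handled compatibly or is captured elsewhere. The formal DLT count behind escalation is unchanged.

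The size is at most 16.7 points per affected patient in a six-patient arm, and less where the safety population of an arm exceeds six. How many patients are affected cannot be derived from the documents. The conclusion assumes only that no unseen guidance already fixes one rule for all sites.

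**What to change.** Reconcile 4.1 with 7.2.1 and 7.2.2 into a single laboratory-AE rule. One way is to add investigator-judged clinical significance as a trigger in 4.1 for laboratory tests and keep the current-diagnosis carve-out. Adopting the narrower rule in both places would also be consistent, but causality and action taken would then go unreported for these events. ECG and vital-sign changes are a separate decision: 7.2.2 covers laboratory values only, so aligning with it does not extend to them.

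Apply the rule to modules not yet locked. SAP IX.C already uses the investigator's evaluation of each result, so values marked clinically significant with no matching AE record can be listed and queried. SAP section I says that Module 1 is locked, so leave its data as they are. State in the SAP or study report which rule governed each module's AE tables, Module 1 included, so that the correction does not itself create an unexplained difference between modules.

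The cost is a wording change, revised CRF guidance, and a few more AE entries and queries. No dose or treatment rule changes.
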